7.5.4 Assessing Relationship to the INTERCEPT Blood System Device

The Clinical Investigator in collaboration with the blood transfusion service staff will assess whether there is a reasonable possibility that the INTERCEPT Blood System for Red Blood Cells medical device used for preparation and or processing of the blood component caused or contributed to an AE. Determination of whether there is a reasonable possibility that an INTERCEPT component caused or contributed to an AE includes assessing whether a device malfunction occurred during the preparation of the blinded study RBC component.

7.5.5 Reporting Requirements

The AE, SAE, and TR collection period will begin at the start of surgery or the first study RBC transfusion, whichever is first. AEs including protocol specified AEs, TRs, and SAEs (see Section 7.3) are collected daily during the acute transfusion support period and as reported through 28 days after the last study transfusion. Each AE is to be assessed to determine if it meets the criteria for an SAE. If an SAE occurs, expedited reporting will follow regional and international regulations, as appropriate. Adverse events (AEs) will not be collected for non-transfused subjects. Vital status will be reported for randomized and non-transfused subjects at the time of discontinuation.

If an SAE occurs, the Investigator must notify Cerus or its designated safety representative within 24 hours after becoming aware of the event by entering in the eCRF. When reporting SAEs to Cerus, the Investigator will ensure the report includes the severity, seriousness criteria or criterion, and causality assessments as detailed in section 7.5.

Recording the data directly into the eCRF is the preferred method to send this information to the

Cerus Corporation

Title: A Randomized, Double-Blinded, Controlled, Parallel Group, Non-inferiority, Phase III Study to Evaluate the Efficacy and Safety of the INTERCEPT Blood System for Red Blood Cells in Patients undergoing Complex Cardiac Surgery Procedures (the ReCePI study)

project contact for SAE receipt. In circumstances where the Investigator is unable to record the data on the eCRF, the Investigator must notify Cerus Product Safety via e-mail or the PPD Hotline within 24 hours of the site's awareness. Sponsor and Contract Research Organization (CRO) contact information is provided in **Table 7.6**.

Table 7.6 Cerus Product Safety Contact Information

Name, Title (Study Role)	Phone	Address
ePIP (protocol inquiries)	N/A	No longer used
PPD Safety Hotline (SAE reporting if Medidata Rave is unavailable)	[contact]	N/A
Cerus Product Safety Team	N/A	[contact]
[name], PhD Sr. Director, Clinical Research & Medical Affairs (Medical Monitor)	[contact]	[contact]
[name], PhD Chief Medical Officer (Back-up Medical Monitor)	[contact]	[contact]

Investigators must also comply with local requirements for reporting SAEs to the Institutional Review Board/Ethics Committee (IRB/EC).

For all SAEs, the Investigator is obligated to pursue and provide information to Cerus or its representative in accordance with the timeframes for reporting specified above. In addition, an Investigator may be requested by Cerus or its designee to obtain specific additional follow-up information in an expedited fashion. This information may be more detailed than that captured on the adverse event case report form. In general, this will include a description of the adverse event in sufficient detail to allow for a complete medical assessment of the case and independent determination of possible causality. Information on other possible causes of the event, such as concomitant medications and illnesses must be provided. In the case of a patient death, a summary of available autopsy findings must be sent as soon as possible to Cerus or its designated representative.

7.5.6 Reporting Device Malfunctions

Blood centers are required to report any malfunctions of the INTERCEPT Blood System for RBCs medical device on the eCRFs. If a device malfunction impacts the

Cerus Corporation

Title: A Randomized, Double-Blinded, Controlled, Parallel Group, Non-inferiority, Phase III Study to Evaluate the Efficacy and Safety of the INTERCEPT Blood System for Red Blood Cells in Patients undergoing Complex Cardiac Surgery Procedures (the ReCePI study)

health of a person (patient, user or other) during the study, it may also be considered an AE/SAE. The Investigator must notify Cerus Product Safety. Sponsor contact information is provided in **Table 7.6**. If a device malfunction occurs at the participating hospitals sites, the site will complete a Device Malfunction Form.

7.6 DATA AND SAFETY MONITORING BOARD (DSMB) AND INTERIM ANALYSIS

The study data and safety will be monitored on a regular basis by an independent Data and Safety Monitoring Board (DSMB). The primary responsibility of the DSMB is to ensure patient safety and review protocol compliance for data collection. The DSMB will be assembled by the Sponsor and composed of transfusion medicine experts, surgeon(s) and a statistician. DSMB members will be independent of the Sponsor. The DSMB will review safety data and make recommendations according to the current DSMB charter.

Aside from the blinded interim analysis for sample size re-estimation performed in October 2021 that resulted in the reduction in study size from 600 to ≥ 292 patients, no other interim analysis is planned for this study to compare treatment differences with respect to efficacy or safety at any time prior to the completion of the study. Specific stopping rules, developed for safety considerations, are defined in Section 4.6.

Cerus Corporation

Title: A Randomized, Double-Blinded, Controlled, Parallel Group, Non-inferiority, Phase III Study to Evaluate the Efficacy and Safety of the INTERCEPT Blood System for Red Blood Cells in Patients undergoing Complex Cardiac Surgery Procedures (the ReCePI study)

8 STATISTICS

8.1 STATISTICAL METHODS

8.1.1 Efficacy Analysis

For the primary efficacy endpoint, the treatment difference (Test – Control) and its two-sided 95% confidence interval (CI) will be estimated from Cochran-Mantel-Haenszel (CMH) test stratified by baseline sCr (sCr \geq 1.2 mg/dL vs. < 1.2 mg/dL) and cardiac surgery group (more at risk for renal complications vs. less at risk) performed. The upper bound of the two-sided 95% CI will be compared with the 50% of the observed Control rate. Non-inferiority will be achieved if the upper bound is less than the 50% of the observed Control rate. For the non-inferiority test, the null and alternative hypotheses (H₀ and H₁, respectively) will be formulated as follows:

$$H_0: P_{Test} - P_{Control} \geq 50\% \times \hat{P}_{Control} \quad vs. \quad H_1: P_{Test} - P_{Control} < 50\% \times \hat{P}_{Control},$$

where P_{Test} and $P_{Control}$ are the event rates for Test (INTERCEPT) and Control groups, respectively, and $\hat{P}_{Control}$ is the observed Control rate.

Same CMH test will be used for assessment of treatment differences for the secondary efficacy endpoints. As a sensitivity analysis, logistic regression will be utilized to estimate the treatment differences after controlling for baseline sCr, cardiac surgery group performed and other covariates to be detailed in the statistical analysis plan (SAP).

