
Study Procedures:
 
Screening/Recruitment
 
In order to minimize the number of patients who enroll in the study but do not require RBC transfusion, only patients with a relatively high likelihood to receive a RBC transfusion as determined by the Investigator (e.g., patients receiving aspirin, clopidogrel (or analogs) and/or GPIIb/IIIa inhibitors), or patients with a TRUST Score of ≥ 3 will be eligible for enrollment. Patients ≥ 11 years of age undergoing complex cardiac surgery may be identified through pre-operative scheduling procedures in advance of their surgery.
 
Patients undergoing urgent or emergent cardiac surgery are eligible for the study, subject to institutional review board (IRB) approval of an appropriate informed consent process.
 
All potentially eligible patients will be approached for study consent/assent within 30 days prior to their surgical procedure. Subjects who consent/assent to the study will be assigned a subject ID number and undergo screening.
 
Screening will include documentation of the patient's pre-surgical exposure to radiographic contrast media and number of prior pregnancies (females). Screening data may be derived from the medical record when performed within 30 days prior to their surgical procedure. Eligibility status and other study data including all TRUST components will be entered into the clinical database via an electronic data capture (EDC) system using electronic case report forms (eCRFs). Patients who fail eligibility for any or multiple inclusion/exclusion criteria may be rescreened for eligibility closer to the time of surgery.
 
Randomization and Blinding
 
Eligible subjects will be randomized up to 7 days before or on the day of scheduled surgery (Day 0). An Interactive Web Response System (IWRS) will be used for electronic randomization of eligible patients. Randomization (in 1:1 ratio for Test:Control) stratified by site, pre-existing renal impairment (baseline sCr ≥ 1.2 mg/dL vs. < 1.2 mg/dL), and cardiac surgery group (more at risk for renal complications vs. less at risk) will be employed. Screened subjects who receive a red cell transfusion prior to randomization will no longer be considered for randomization, and their participation in the study will end. Patients may be rescreened for eligibility closer to the time of surgery.
 
Treatment
 
Once a subject is randomized, only study RBCs (Test or Control, per the subject's randomization) should be dispensed and transfused during the acute transfusion support period (Day 0 to Day 7 post surgery, hospital discharge, or death, whichever is first), as clinically indicated and determined by the treating physician.
 
In rare exceptions where study RBCs are unavailable or patient's need for RBC transfusions exceeds the quantity of study RBCs in inventory at the hospital blood bank (e.g., during a Massive Transfusion Protocol), a
					

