4.3 RANDOMIZATION AND BLINDING

Potentially eligible subjects will be screened and will be considered for randomization. If a subject is screened and receives a RBC transfusion prior to randomization, that subject will no longer be considered for randomization, and their participation in the study will end. Patients may be rescreened for eligibility closer to the time of surgery. An Interactive Web Response System (IWRS) will be used for electronic randomization of eligible patients. Following screening and prior to surgery (up to 7 days before surgery or day of surgery but before start of surgical procedure), the subject's eligibility status will be re-checked and entered in the eCRF. If eligible, the subject will be randomized with a 1:1 ratio for Test:Control within his/her randomization stratum. Randomization will be stratified by site, pre-existing renal impairment ($sCr \geq 1.2 \text{ mg/dL}$ vs. $< 1.2 \text{ mg/dL}$), and surgery group based on less (# 1-3 below) vs. more (#4-7 below) risk for renal complications (based on Mehta 2006 and expert opinion).

Less Risk

1. Single Vessel Coronary Artery Bypass Graft, first or repeat procedure
2. Multiple Coronary Artery Bypass Grafts, first or repeat procedure
3. Single Valve Repair or Replacement, first or repeat procedure

More Risk

4. Multiple Valve Repair or Replacement, first or repeat procedure
5. Surgery involving both Coronary Artery Bypass Graft(s) and Valve Repair(s), first or repeat procedure
6. One or more of the following procedures, with or without Coronary Bypass Graft(s):
 - Left ventricular aneurysm repair,
 - Ventricular and/or atrial septal defect repairs,
 - Batista procedure (surgical ventricular remodeling),
 - Surgical ventricular restoration,
 - Congenital cardiac defect repair,
 - Aortic procedures,
7. Other complex cardiac surgery or thoracic aorta surgery procedures not listed above

Cerus Corporation

Title: A Randomized, Double-Blinded, Controlled, Parallel Group, Non-inferiority, Phase III Study to Evaluate the Efficacy and Safety of the INTERCEPT Blood System for Red Blood Cells in Patients undergoing Complex Cardiac Surgery Procedures (the ReCePI study)

Patients undergoing urgent or emergent cardiac surgery are eligible for the study, subject to institutional review board (IRB) approval of an appropriate informed consent process.

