Eligible subjects will be randomized up to 7 days before or on the day of surgery, but prior to the start of surgery (i.e., induction of anesthesia). The adverse event collection period will begin at the beginning of surgery or the first study RBC transfusion, whichever is first.

Cerus Corporation

Title: A Randomized, Double-Blinded, Controlled, Parallel Group, Non-inferiority, Phase III Study to Evaluate the Efficacy and Safety of the INTERCEPT Blood System for Red Blood Cells in Patients undergoing Complex Cardiac Surgery Procedures (the ReCePI study)

For non-transfused subjects, a blood sample for sCr will be drawn at 48 ± 4 hours. Daily sCr assessments will be recorded up to and including 48 ± 4 hours post surgery. Other post baseline laboratory parameters and Adverse events (AEs) will not be collected for non-transfused subjects. Vital status will be recorded at the time of discontinuation.

The complete list of baseline assessments to be performed pre-operatively on the day before or on the day of surgery before surgery commences are outlined in Table 7.1b.

6.1.2 Acute Transfusion Support Period (Surgery [Day 0] to Post-operative Day 7, Hospital Discharge or Death, Whichever is First)

The complete list of assessments to be performed during the acute transfusion support period are outlined in Table 7.1c.

During the acute transfusion support period (Day 0 to Day 7), hospital discharge or death, whichever is first, patients will be transfused with Test or Control RBCs. Induction and end of anesthesia are considered start and stop time of surgery. All transfusions administered through Day 7 will be of the assigned treatment arm as often as feasible without compromising patient care.

A screen for antibodies specific for INTERCEPT RBCs should be performed every time that a routine IAT is performed during the acute 7-day study transfusion period.

A blood sample for sCr will be taken at $48 (\pm 4$ hours) after completion of surgery, and sCr will be determined on a daily basis during the acute transfusion support period up to 7 days post-surgery. Other parameters will be collected on eCRFs only when available in the medical record.

Randomized subjects who do not receive an RBC transfusion following randomization within the first 48 hours after surgery will be discontinued from the study and replaced.

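### The primary CMH test and the logistic sensitivity model use the surgery group as performed, which is settled after randomisation, rather than the scheduled-surgery stratum used to randomise

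*Protocol*

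**What the plan says.** Section 8.1.1 names two stratifiers for the primary CMH test: creatinine at a 1.2 mg/dL cut-off and the "cardiac surgery group (more at risk for renal complications vs. less at risk) performed". The logistic sensitivity model estimates the treatment difference "after controlling for baseline sCr, cardiac surgery group performed and other covariates". The synopsis, under Statistical methods, has the same text. Only the further covariates of the logistic model are left to the SAP.

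On allocation, Section 4.3 states: "Randomization will be stratified by site, pre-existing renal impairment", and surgery group (less or more risk for renal complications). On timing, Section 6.1.1 states: "Eligible subjects will be randomized up to 7 days before or on the day of surgery, but prior to the start of surgery". Table 7.1a collects the type of scheduled surgery at screening. Section 6.1.2 and Table 7.1c collect the details of the procedure separately, in the surgical period. Under Section 4.4, study transfusion can begin from surgery on Day 0.

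For creatinine, the synopsis describes the allocation factor as follows: "Randomization (in 1:1 ratio for Test:Control) stratified by site, pre-existing renal impairment (baseline sCr ≥ 1.2 mg/dL vs. < 1.2 mg/dL". Section 2.5 also places this stratum at baseline.

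**The concern.** A stratifier fixed before treatment cannot be affected by it. The procedure performed does not have that protection. It is always settled after randomisation, and transfusion during the operation may already have begun. The boundary between the risk groups in Section 4.3 is easy to cross: a single-valve operation (item 3, less risk) to which a bypass graft is added becomes item 5 (more risk).

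If the product affected the intra-operative course, and through it the procedure, some Test patients would move to the higher-risk stratum because of the treatment. They would then be compared with Control patients at higher risk for other reasons, and part of a true excess on Test would disappear from the stratified difference. In a non-inferiority trial that pulls towards success.

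There is also a loose end inside the protocol. Section 8.1.3 defines subgroups by the randomisation stratification variables, while 8.1.1 does not use that term. Read literally, the primary and subgroup analyses could group the same patient differently.

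**Working it through.** **1. The plan's own figure.** Inputs from Section 8.2: Control rate 0.30, margin 50% × 0.30 = 0.15, true difference 0, two-sided alpha 0.05, 146 per arm.

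- n per arm = 2 × 0.30 × 0.70 × (1.960 + 0.842)² / 0.15² = 0.42 × 7.85 / 0.0225 ≈ 146.5, so 147 (294 in total, against 292 stated).
- Power at 146 per arm = Φ(0.15 / √(0.42/146) − 1.960) = Φ(2.797 − 1.960) = 79.9%.

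The stated size is reproduced. No stratum enters the formula, so the choice of strata leaves 292 unchanged.

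**2. Timing side by side.**

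| Item | When it is known | Source |
|---|---|---|
| Scheduled procedure | Screening | Table 7.1a |
| Randomisation | Day −7 to Day 0, before induction | Sections 4.3, 6.1.1 |
| First study transfusion | From surgery, Day 0 | Section 4.4 |
| Procedure performed | During or after surgery | Section 6.1.2, Table 7.1c |

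The performed group follows randomisation for every patient. It follows first exposure for some.

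**3. If procedure changes depend on arm.** Simulation of 292 patients, 4,000 runs per case, Mantel-Haenszel risk difference. The upgrade rates, and a 25-point higher risk in patients upgraded because of complications, are assumptions; the protocol gives neither.

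| Upgraded, Control / Test | As-randomised strata (points) | As-performed strata (points) | Hidden (points) |
|---|---|---|---|
| 5% / 5% | 0.0 | 0.0 | 0 |
| 10% / 10% | 0.04 | 0.04 | 0 |
| 5% / 10% | 1.46 | 1.14 | 0.32 |
| 5% / 15% | 2.40 | 1.72 | 0.68 |

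The hidden part is 22% to 28% of the difference (0.32/1.46 and 0.68/2.40). Against the 15-point margin it is 2% to 5% (0.32/15 and 0.68/15).

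**4. If reclassification is independent of arm.** A second simulation (10,000 runs per setting, 292 patients) used D = Σ wₖ(p₁ₖ − p₀ₖ) / Σ wₖ with wₖ = n₁ₖn₀ₖ/(n₁ₖ + n₀ₖ). It applied the protocol's rule that D + 1.96·SE must be below half the observed Control rate. Assumed: half of patients in the more-risk surgery group, 30% with creatinine at or above 1.2 mg/dL, a rate spread between strata of 15 or 25 points, and the same reclassification rate on both factors.

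| Spread | Reclassified | Power, as-randomised | Power, actual | Loss (points) |
|---|---|---|---|---|
| 15 | 5% | 76.2% | 76.5% | 0.2 |
| 15 | 10% | 76.5% | 76.8% | 0.3 |
| 15 | 20% | 76.0% | 77.0% | 1.1 |
| 25 | 5% | 79.2% | 80.3% | 1.0 |
| 25 | 10% | 78.6% | 80.2% | 1.7 |
| 25 | 20% | 77.1% | 80.0% | 3.0 |

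Losses are computed before rounding. Bias is about zero with either set of strata. At a true rate ratio of 1.5, the two rejection rates differ by 0.3 points or less. Because both factors are reclassified together, the losses are not those of surgery group alone. The absolute power levels also reflect the use of the observed Control rate as the margin, which is a separate matter.

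**The case against.** The textual evidence is one word. In the CMH sentence it trails a long parenthesis and could be read as belonging to the test. That reading is not available in the logistic sentence, where the word attaches directly to the surgery group, and the synopsis repeats both sentences.

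Handling a mismatch between the allocated and the actual stratum is ordinary SAP content, and the SAP is not shown. It may well deal with this. But the protocol itself fixes the two stratifiers and defers only other covariates, so its wording can be questioned as it stands.

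The route to bias is narrow. Section 4.3 keeps operating-room and surgical staff blinded, so nobody can choose a procedure by arm. Only a real product effect on the course of the operation could do it, and nothing in the protocol suggests one. This stands, and it limits the size of the point.

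A reader might infer that the creatinine stratifier also departs from the randomisation stratum. Section 6.1.1 describes "The complete list of baseline assessments to be performed pre-operatively on the day before or on the day of surgery", so that value can postdate a randomisation done days earlier. The documents do not support the inference. The synopsis and Section 2.5 call the randomisation stratum baseline creatinine too, with the same cut-off, and Table 7.2 allows screening and baseline samples to be one and the same on Day −1 or Day 0. Which value is meant is unclear; no different value is stated. A pre-surgery value also precedes study transfusion, except in what the synopsis treats as a protocol deviation, so there is hardly any route to bias through it.

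**Conclusion.** The point holds for surgery group and is minor. As worded, the primary CMH test and the logistic model use a grouping settled after randomisation, possibly after exposure, where the allocation grouping was available.

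A reader might go further and conclude that the primary result is biased towards non-inferiority. That does not follow. With arm-independent changes there is no bias. The shift of about 0.3 to 0.7 points requires upgrades two to three times as frequent on Test and an assumed 25-point excess risk, and it remains small beside a 15-point margin. Nor is the as-randomised choice free: under the assumed reclassification rates it gives up about 0.2 to 3 points of power. The case for it is that the primary test then rests on a variable the product cannot touch.

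**What to change.** In Section 8.1.1 and in the synopsis under Statistical methods, state that the surgery-group stratum in the primary CMH test is the one recorded in the IWRS at randomisation. Keep the as-performed group as a labelled sensitivity analysis, and have the logistic model say which grouping it uses.

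Use the IWRS-recorded creatinine stratum in the CMH test as well, which settles the ambiguity over baseline. Do not add to Section 4.3 a statement of which creatinine value the IWRS used: enrolment began in November 2018, the protocol does not say which value was entered, and the statement could be wrong.

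The cost is a change of wording in the protocol, carried through to the SAP, with no new data and no change to the planned 292 patients. The possible small loss of power described above should be accepted knowingly.

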
Transfusion reactions (as defined by the CDC National Healthcare Safety Network [NHSN] Hemovigilance Module protocol) through 28 days after last study transfusion.Treatment-emergent immunization to RBC allo-antigens through 28 ± 3 days after the last study transfusion.Treatment-emergent immunization to HLA allo-antigens through 28 ± 3 days after the last study transfusion.						
Statistical methods: For the primary efficacy endpoint, the treatment difference (Test – Control) and its two-sided 95% confidence interval (CI) will be estimated from Cochran-Mantel-Haenszel (CMH) test stratified by baseline sCr (sCr ≥ 1.2 mg/dL vs. < 1.2 mg/dL) and cardiac surgery group (more at risk for renal complications vs. less at risk) performed. The upper bound of the two-sided 95% CI will be compared with the 50% of the observed Control rate. Non-inferiority will be achieved if the upper bound is less than the 50% of the observed Control rate. For the non-inferiority test, the null and alternative hypotheses (H_0 and H_1 , respectively) will be formulated as follows: $H_0: P_{Test} - P_{Control} \geq 50\% \times \hat{P}_{Control}$ vs. $H_1: P_{Test} - P_{Control} < 50\% \times \hat{P}_{Control}$, where P_{Test} and $P_{Control}$ are the event rates for Test (INTERCEPT) and Control groups, respectively, and $\hat{P}_{Control}$ is the observed Control rate. Same CMH test will be used for assessment of treatment differences for the secondary efficacy endpoints. As a sensitivity analysis, logistic regression will be utilized to estimate the treatment differences after controlling for baseline sCr, cardiac surgery group performed and other covariates to be detailed in the statistical analysis plan (SAP). Treatment-emergent AEs (defined as AEs with an onset date/time that is on or after the start date/time of the first study transfusion) will be summarized by treatment group, system organ class (SOC), and preferred term. Subgroup analysis by the randomization stratification variables (clinical site, pre-surgery renal impairment, and cardiac surgery group) and by demographic variables such as age group (≤ 18 , 19 to 65, and > 65 years old), sex, and race will be presented for primary and secondary efficacy endpoints. Additional subgroup analysis may also be presented as suggested by the data.						

Cerus Corporation

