Cr Increase ≥ 0.3 mg/dL	7 (22.6%)	10 (35.7%)	2 (50.0%)	3 (30.0%)	10 (27.8%)	10 (29.4%)	20 (27.0%)	25 (33.8%)	45 (30.4%)

CLI 00070 and RBC 3A	Valve Only		CABG Only		Valve and CABG		All Patients		
	Test	Control	Test	Control	Test	Control	Test	Control	Total
	(N=41)	(N=36)	(N=16)	(N=23)	(N=39)	(N=39)	(N=99)	(N=100)	(N=199)
Cr Increase ≥ 0.1 mg/dL	23 (56.1%)	19 (52.8%)	8 (50.0%)	9 (39.1%)	27 (69.2%)	25 (64.1%)	60 (60.6%)	55 (55.0%)	115 (57.8%)
Cr Increase ≥ 0.2 mg/dL	16 (39.0%)	15 (41.7%)	5 (31.3%)	7 (30.4%)	18 (46.2%)	21 (53.8%)	40 (40.4%)	45 (45.0%)	85 (42.7%)
Cr Increase ≥ 0.3 mg/dL	12 (29.3%)	12 (33.3%)	2 (12.5%)	4 (17.4%)	11 (28.2%)	12 (30.8%)	26 (26.3%)	30 (30.0%)	56 (28.1%)

Notes:

* Included patients with "Other" type of surgery.

Cerus Corporation

Title: A Randomized, Double-Blinded, Controlled, Parallel Group, Non-inferiority, Phase III Study to Evaluate the Efficacy and Safety of the INTERCEPT Blood System for Red Blood Cells in Patients undergoing Complex Cardiac Surgery Procedures (the ReCePI study)

Based on these data, Cerus proposed a non-inferiority design in ReCePI to rule out an increase of $\Delta sCr \geq 0.3 \text{ mg/dL}$ more than 50% from the Control rate with approximately 80% power and one-sided alpha of 2.5%. This is based on a Control rate of $\Delta sCr \geq 0.3 \text{ mg/dL}$ of 30%. At least 292 subjects will be randomized and transfused.

Randomization (in 1:1 ratio for Test:Control) stratified by site, pre-existing renal impairment (stratum with either $sCr \geq 1.2 \text{ mg/dL}$ or $sCr < 1.2 \text{ mg/dL}$ at baseline), and cardiac surgery risk level (high or low risk stratum group 1 or 2, respectively) will be employed.

As per Lassnigg et al (2004 and 2008) patients who die within 48 hours of the end of surgery and have received at least one study transfusion will be included in the modified intent-to-treat (mITT) analysis but excluded from the per protocol analysis. Patients who have not received a study transfusion within 48 hours of surgery will be excluded from the analysis and replaced.

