4 INVESTIGATIONAL PLAN

4.1 ENDPOINTS

4.1.1 Primary Endpoints

The primary efficacy endpoint is the proportion of patients, who have received at least one study transfusion with a diagnosis of renal impairment defined as:

- Any raised sCr level, occurring after transfusion of a study RBC, of ≥ 0.3 mg/dL (or 26.5 μ mol/L) from the pre-surgery baseline within 48 ± 4 hours of the end of surgery.

If any subject meets this criterion before receiving a study transfusion, that particular event will not be included in the primary endpoint analysis. The treatment comparison for the primary efficacy endpoint will be assessed by a non-inferiority test (Test–Control) with a non-inferiority margin of 50% increase from the Control rate and two-sided 0.05 alpha level. Patients who receive a study transfusion but die within 48 hours after surgery will be included in the mITT analysis but excluded from the per protocol analysis.

The primary safety endpoints are:

- Proportion of patients with any treatment-emergent adverse events (TEAEs) possibly, probably or definitely related to study RBC transfusion through 28 days after the last study transfusion; and
- Proportion of patients with treatment-emergent antibodies with confirmed specificity to INTERCEPT RBCs by end of study (i.e., 75 ± 15 days after the last study transfusion).

TEAEs by definition will comprise all untoward medical events occurring after the start of the first study RBC transfusion and during the study (i.e., adverse events, serious adverse events, unanticipated adverse device effects, TRs and within 28 days post last study RBC transfusion). The primary safety endpoint is focused on possibly, probably or definitely related adverse events to the study RBC transfusion, because these patients have many adverse events which are unrelated to study RBC transfusion.

Cerus Corporation

Title: A Randomized, Double-Blinded, Controlled, Parallel Group, Non-inferiority, Phase III Study to Evaluate the Efficacy and Safety of the INTERCEPT Blood System for Red Blood Cells in Patients undergoing Complex Cardiac Surgery Procedures (the ReCePI study)

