8.2 DETERMINATION OF SAMPLE SIZE

A total of at least 292 transfused subjects, approximately 146 per arm, are planned to generate sufficient efficacy and safety data for the Test and Control components in patients undergoing cardiac surgery procedures.

For the primary efficacy endpoint, a non-inferiority test will be conducted to assess for treatment difference (Test – Control). By assuming the proportion of patients with $\Delta sCr \geq 0.3\text{mg/dL}$ to be 30% in the Control arm and no more than 50% increase from the Control rate as the non-inferiority margin, a sample size of 292 patients (146 per arm) will provide approximately 80% power to declare non-inferiority at the two-sided 0.05 alpha level, assuming the true treatment difference is zero.

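### The non-inferiority rule treats a margin estimated from the Control arm as known: one-sided error is about 5.8% instead of 2.5%, and the stated 80% power belongs to a different test

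*Protocol*

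**What the plan says.** Section 8.1.1, repeated under Statistical methods in the synopsis, sets the decision rule. The Test minus Control difference and its two-sided 95% interval come from a Cochran-Mantel-Haenszel analysis stratified by baseline creatinine and surgery group. Then: "The upper bound of the two-sided 95% CI will be compared with the 50% of the observed Control rate", and "Non-inferiority will be achieved if the upper bound is less than the 50% of the observed Control rate". The null and alternative hypotheses are written with the observed Control rate (P-hat) on the right-hand side.

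Elsewhere the margin is a statement about the Control rate itself. Section 4.1.1 gives a "non-inferiority margin of 50% increase from the Control rate and two-sided 0.05 alpha level", and section 7.2.1 says the same. Section 2.5 claims "approximately 80% power and one-sided alpha of 2.5" percent. Section 8.2 takes the event proportion "to be 30% in the Control arm and no more than 50% increase from the Control rate as the non-inferiority margin". It says that the planned enrolment, 146 in each group and 292 altogether, "will provide approximately 80% power to declare non-inferiority at the two-sided 0.05 alpha level, assuming the true treatment difference is zero". The synopsis repeats that power statement.

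No section adds the sampling error of the observed margin to the interval or to the sample size, and none fixes the margin at 15 points.

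**The concern.** A margin proportional to the Control rate is legitimate, but when it is estimated from the trial its uncertainty has to enter the test. Here it does not. A Control arm that by chance runs high helps twice: it lowers the observed difference and it widens the margin. The two effects reinforce each other, so the interval is too short for the comparison being made.

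The hypotheses are also not well formed. A null hypothesis containing a sample statistic makes no claim about the population, so no error rate can be attached to it as written.

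This is the only confirmatory efficacy test in a study meant to support licensure. The stakes are a false-positive rate more than twice the stated one for a true 50% excess of renal impairment, and a power figure calculated for a rule that will not be applied.

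**Working it through.** **Inputs** (protocol 2.5, 4.1.1, 8.1.1, 8.2): n = 146 per arm, 1:1 allocation; Control rate pC = 0.30; margin 50% of the Control rate; one-sided 2.5%, z = 1.96; no true difference for power. Error is evaluated at the boundary of the section 4.1.1 margin, pT = 1.5 × 0.30 = 0.45.

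**1. The plan's own figure.** With a fixed margin of 0.15, SE = √(2 × 0.30 × 0.70 / 146) = 0.0536. Power = Φ(0.15/0.0536 − 1.96) = 79.9%. Exact enumeration of two Binomial(146) arms gives power 80.1% and error 2.4%. The stated 80% is therefore correct for a fixed 15-point margin.

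**2. What the written rule tests.** The rule is p̂T − p̂C + 1.96·SE < 0.5·p̂C, which rearranges to p̂T − 1.5·p̂C + 1.96·SE < 0.

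- Variance carried by the interval: Var(p̂T) + Var(p̂C).
- Variance of the quantity compared with zero: Var(p̂T) + 2.25·Var(p̂C).

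**3. Error at pC = 0.30, pT = 0.45.**

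- SE used: √((0.2475 + 0.21)/146) = 0.0560.
- True SE: √((0.2475 + 2.25 × 0.21)/146) = 0.0702.
- Effective critical value: 1.96 × 0.0560/0.0702 = 1.56.
- Error: Φ(−1.56) = 5.9%; by exact enumeration 5.8%.

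The exact error is 5.7% to 5.9% for Control rates from 15% to 40%. It is still 5.8% at 239 per arm, because the ratio of the two standard errors does not depend on n.

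**4. Power of the written rule with no true difference.** The true SE is √(3.25 × 0.21/146) = 0.0684. Power = Φ((0.15 − 1.96 × 0.0536)/0.0684) = Φ(0.656) = 74.4%; exact 74.6%. At other Control rates the exact power is 55.6% (20%), 65.8% (25%) and 82.2% (35%).

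**5. Tests that carry the margin's variance** (146 per arm, 30% Control rate, exact, unstratified):

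| Test | Error at RR 1.5 | Power at RR 1 |
|---|---|---|
| Rule as written | 5.8% | 74.6% |
| Log relative-risk upper limit < 1.5 | 2.7% | 61.9% |
| Upper limit of pT − 1.5·pC < 0 | 2.3% | 59.3% |

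**6. An example.** Take 44/146 Control events (30.1%), so the observed margin is 15.07 points. With 50/146 Test events the difference is 4.11 points and its upper limit 14.82 points, so the rule declares non-inferiority. The relative risk in the same data is 1.14 with an upper 95% limit of 1.59, so an excess above 50% has not been excluded. Both valid tests stop at 46 Test events.

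**7. Stratification.** The protocol gives no stratum sizes or rates. Under assumed shares of 35/35/15/15% and three sets of assumed stratum rates (overall Control rate 28.5% to 30%), simulation of the Mantel-Haenszel rule gave error of 6.0% to 6.2% and power of 75% to 76%. Stratifying does not remove the problem.

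**The case against.** The strongest objection is that 5.8% is measured against a null the protocol does not literally write: section 8.1.1 puts the observed rate in the hypothesis. That is true, and the figure rests on reading the margin as sections 4.1.1 and 7.2.1 define it, relative to the true Control rate. The literal alternative has no defined error rate, so it cannot support the claimed 2.5% either.

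Second, the power shortfall of the rule as written is modest, about 5 points, and 292 is described as a minimum. This stands. The larger drop, to 59% to 62%, appears only once the error is corrected, and the two should be reported separately.

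Third, a fixed 15-point margin would also restore consistency, with 2.4% error and 80.1% power at 146 per arm. It is a coherent option but a different margin. At a 20% Control rate it tolerates a 75% relative increase (0.15/0.20), which departs from the stated 50%.

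Fourth, the relative-risk limit and the linear contrast differ somewhat in error and power, and the relative-risk version runs slightly above nominal at 2.7%. This also stands, so one method has to be named in advance.

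Deferral to the SAP is not an answer. Section 8.1.1 leaves only the further covariates of the logistic sensitivity analysis to that document; the interval, comparator and success criterion are fixed in the protocol.

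**Conclusion.** The point holds. With 146 per arm and a 30% Control rate, the written rule has a one-sided error of 5.8% at a true 50% relative excess, against a stated 2.5%. Its power with no true difference is 74.6%, against about 80%. A test of the same margin with error near nominal has power of about 59% to 62% at this sample size. The sample-size arithmetic is correct in itself; the fault is that section 8.2 sizes one test and section 8.1.1 performs another.

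These figures assume two independent binomial arms, equal allocation and the margin as section 4.1.1 defines it. The error result hardly depends on the Control rate; the power results do.

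**What to change.** Keep the 50% relative margin and state it in parameters: H0: P_T/P_C ≥ 1.5 against H1: P_T/P_C < 1.5. Declare non-inferiority if the upper limit of the two-sided 95% interval for the Mantel-Haenszel relative risk (same four strata, Greenland-Robins variance) is below 1.5. The upper limit of P_T − 1.5·P_C, with the factor 2.25 on the Control variance, is an acceptable and slightly more conservative alternative. Prespecify one of the two and quote that test's own power: about 62% for the relative risk, or 59% for the contrast. Report the risk difference descriptively. The logistic sensitivity analysis would best report a standardised relative risk, so that it faces the same margin.

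The edits fall in the synopsis, sections 2.5, 4.1.1, 7.2.1, 8.1.1 and 8.2, and the SAP. They need no new data or patients, but the stated power becomes less favourable.

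If 80% power is still wanted at a 30% Control rate, the normal approximations give:

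- relative risk: (1.96 + 0.84)² × 2 × (0.70/0.30) / (ln 1.5)² ≈ 223 per arm (446 in total);
- linear contrast: 3.25 × 0.21 × (1.96 + 0.84)² / 0.15² ≈ 239 per arm (478 in total).

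If the sponsor prefers a fixed 15-point margin, the existing sample size stands, but the protocol must then drop the relative definition and justify the absolute one.
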